## **9. RESEARCH DESIGN AND METHODS**

**Overall Study Design.** The clinical trial will be registered under [www.clinicaltrials.gov](http://www.clinicaltrials.gov). Subjects between the ages of 18-65 who have a POTS diagnosis will be enrolled. Specifically, we will enroll patients who have hyperadrenergic POTS as confirmed by norepinephrine (NE) levels > 600 pg/ml. This is a 3-month study with a randomized double-blind placebo controlled cross over design. Subjects will be randomized into one of two groups (Ivabradine or placebo for one-month) then crossed over after a one-week washout period to the other group for one-month. Refer to Figure 1 below for details.

[figure not shown]

Figure 1. Randomized double-blind placebo-parallel group crossover trial with Ivabradine for patients with POTS.

**Study Visits.** There will be seven visits at the ACTRI and UCSD Cardiology clinics.

-Visit 1 is the pre-screening visit during which norepinephrine (NE) blood results will be obtained to confirm hyperadrenergic POTS diagnosis (NE> 600pg/ml). Orthostatic heart rate will be monitored. A urine pregnancy test will also be administered at this time. Post-menopausal women and women who are infertile will not be asked to take pregnancy test per PI discretion.

-At Visit 2, baseline lab work will be obtained to assess cardiometabolic health (CBC, CMP, TSH, T4, BNP). A tilt table test will be performed to determine baseline heart rate and QOL questionnaire (ShortForm36, SF36) will be completed. Orthostatic heart rate will be monitored. At this point, the patient will be randomized into the Ivabradine or placebo group for one month.

-At Visit 3, two-weeks into treatment, the patient will return to ACTRI for drug titration. Orthostatic heart rate will be monitored. If the patient fulfills criteria (see **Ivabradine Dosing** below), they will either increase, decrease, stop, or not change their Ivabradine dose.

-At Visit 4, one month after starting the current treatment, orthostatic heart rate monitoring, NE bloodwork, and QOL questionnaires will be completed. There will be a one-week wash-out period before the patient crosses over to the other group for one month.

-At Visit 5, the patient will return for orthostatic heart rate monitoring, NE bloodwork, and QOL questionnaires. A urine pregnancy test will be administered at this time. Post-menopausal women and women

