**Specific Protocols.** Brief synopsis of methods currently used is provided below.

**Tilt Table Test:** Only the physician PIs will perform the tilt table test with assistance from the medical staff of the UCSD Medical Center.

**Orthostatic Heart Rate Monitoring:** First, the patient's heart rate will be measured at rest after lying down for 3 minutes. Then, the patient will be asked to stand and the standing heart rate will be measured after 3 minutes. The changes in position with 3 minute intervals will establish the orthostatic heart rate.

**Quality of Life (QOL) Questionnaire:** Patients will complete the Short Form-36 (SF36) subjective questionnaire to aid in analysis of patient symptoms before/after each treatment period.

**Blood Tests:** The following blood tests will be processed at UCSD Clinical Laboratories: 1) Cardiometabolic parameters: (CBC, CMP, TSH, T4, BNP) and 2) norepinephrine levels (NE).

The 2-3-month time period will be used as prior literature suggests that this length of therapy is needed to trigger pharmaceutical changes to translate into functional endpoints.

**Assessments.** We will assess for patient improvement with tilt table testing, orthostatic heart rate monitoring, labs, and quality of life (QOL) questionnaires before and after treatment. The patient will undergo a baseline norepinephrine workup and a baseline tilt table test; if the patient is on Midodrine, Florinef, or Ivabradine, there will be a one week washout period. The patient will then be randomized into the Ivabradine or the placebo group for one month. After this one month, they will undergo orthostatic heart rate monitoring, blood work for norepinephrine levels, and QOL questionnaires. There will be a one week washout period before they are crossed over to the other therapy (placebo vs Ivabradine) for one month. The washout period protocol

---

includes maintaining a stable salt and fluid intake. Once crossed over, they will repeat an orthostatic heart rate monitoring, blood work for norepinephrine levels, and QOL questionnaires.

We will continuously assess for all adverse events throughout the study. Some of these labeled adverse reactions may include bradycardia, hypertension, atrial fibrillation, and visual distortions (visual brightness, diplopia, visual impairment, phosphenes).

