## 10. HUMAN SUBJECTS

The study aims for 20 adult volunteers (18-65 years) to complete the study. Given the NE inclusion criteria, we will need to enroll at least 60 participants to have 20 participants pass the study screening criteria. With an expected drop-out of 10% after enrollment, this will provide 18 subjects for final analysis, which provides adequate power to detect a significant improvement in decreasing average heart rate at the 0.05 level (see power analysis, above). Participants will be screened and must meet inclusion and exclusion criteria before they are enrolled into the study. We will recruit patients from the cardiology and internal medicine clinics at UCSD Medical Center; in addition, we will utilize the bioinformatics report generated from EPIC and ResearchMatch to assist in recruitment. The main sites of the clinical testing will be conducted at the ACTRI and UCSD Cardiology clinics.

Inclusion/exclusion criteria are below:

1) Inclusion:

- a. Subjects aged 18-65
- b. Subjects must have POTS diagnosis (Hyperadrenergic Subtype with NE > 600pg/ml)
- c. Subjects with norepinephrine levels greater than 600 pg/ml
- d. Subjects with normal CBC, metabolic, and thyroid levels

2) Exclusion:

- a. Uncontrolled arrhythmias
- b. History of thyroid disease requiring dose titration of thyroid replacement medication(s) within the past 3 months (i.e. hypothyroidism on a stable dose of thyroid replacement therapy is not an exclusion)
- c. Drugs that interfere with Ivabradine (example: Cytochrome P450 drugs).
- d. Presentation of peripheral edema and discolored toes with peripheral autonomic neuropathy. Symptoms include: legs (reduced hair growth, cramps), toes (blue color), legs/feet (wounds, ulcers that do not heal), and muscles (numbness, heaviness).
- e. Subjects who have had a history of systemic illnesses (acute or chronic infectious); active and/or uncontrolled autoimmune/inflammatory disease, COPD, anemia, or diabetes.
- f. History of malignancy undergoing active treatment, except non-melanoma skin cancer.
- g. Uncontrolled psychiatric disorder (including history of hospitalization for psychiatric illness).
- h. Subjects with resting heart rate <60beats/min, atrial fibrillation, advanced AV blocks, sinus disease, and acute decompensated heart failure and severe hepatic impairment.
- i. Smokers or alcohol abuse.
- j. Pregnant or breastfeeding mothers.

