### 14. POTENTIAL RISKS

1. Ivabradine: Labeled side effects include: bradycardia, hypertension, atrial fibrillation, and visual distortions (visual brightness, diplopia, visual impairment, phosphenes).
2. Venipuncture: pain, a bruise at the point where the blood is taken, discoloration, redness and swelling of the vein and infection.
3. Tilt table test: Patient will lie flat on a table and straps will be secured. After 15 minutes, the table will be quickly tilted to raise the body to stimulate a change in position like standing. Patient will remain secured and in “standing” position for up to 45 minutes, while being monitored continuously. Only qualified medical professionals will perform this test. There may be an increased risk of prolonged hypotension or tachycardia when in “standing” position. These minor complications improve once the table is returned to the horizontal position.
4. Orthostatic heart rate monitoring: Only qualified medical professionals will perform this test. There may be an increased risk of hypotension or tachycardia upon changing positions from laying down to sitting to standing. Patient will be monitored to avoid such risks and treatment will be provided if necessary to return patient to resting heart rate.
5. Quality of life (QOL) questionnaire: Although there are no known adverse risks, some patients may experience frustration, stress, discomfort, fatigue and boredom. These risks will be addressed by informing participants in advance and allowing them to stop or pause the questionnaire at any time if they wish, and resume when they are ready.
6. Washout Period: The washout period may increase risks of cardiovascular events, such as tachycardia.
7. A potential loss of confidentiality: The UCSD Institutional Review Board (IRB), the FDA, and other government agencies may inspect the study records. To minimize the risk of a potential loss of confidentiality, subjects will be assigned a unique subject code and their blood samples will be assigned a different unique specimen code. A separate paper document will link patient identifiers with subject codes and specimen codes. This document will be kept in a secure location in a locked cabinet. Only the PI and study coordinator will have the key to the cabinet. No research documents will have any patient identifiers and will only be labeled with the unique assigned subject codes.

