  - b. In the event of an AE that occurs during the appointment, the facility is equipped with trained medical staff (physicians and nurses) who can respond quickly. Should an event occur, [name] and the nurses will be nearby to administer immediate medical care and send the patient to the nearest hospital. If the AE occurs after the appointment, the patient will be referred for prompt medical attention. The patient will be withdrawn from the study. [name] will monitor the patient until the problem has been resolved or has stabilized.
3. Orthostatic heart rate monitoring:

- a. Prior to enrollment, the patient will be informed about the risks of orthostatic heart rate monitoring. The physician will comfort the patient to reduce anxiety/fear in order to minimize the probability of a vasovagal response. [name] will continuously monitor and oversee the procedure by checking vital signs. The patient may contact [name] for further questions/concerns.
  - b. In the event of an AE that occurs during the appointment, the facility is equipped with trained medical staff (physicians and nurses) who can respond quickly. Should an event occur, [name] and the nurses will be nearby to administer immediate medical care and send the patient to the nearest hospital. If the AE occurs after the appointment, the patient will be referred for prompt medical attention. The patient will be withdrawn from the study. [name] will monitor the patient until the problem has been resolved or has stabilized.
4. Consuming Ivabradine
- a. [name], a cardiologist, will give the patients specific instructions on the amount of ivabradine capsules they would need to consume each day. A research person will follow up with the patient the next day and once a week for the next 90 days to assess the patient's condition. The patient's conditions will be reported back to the PI. If the patients have reasons to believe that Ivabradine is causing any discomfort, consumption of the capsule will be stopped.

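### Blood pressure and heart rhythm are not specified, recorded or analysed at any visit, although hypertension and atrial fibrillation are listed ivabradine reactions; the vital-sign checks in the safety section do not fill the gap

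*Combined protocol and SAP*

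**What the plan says.** **Risks named.** Section 9, Assessments: "Some of these labeled adverse reactions may include bradycardia, hypertension, atrial fibrillation, and visual distortions". Section 14, item 1, repeats the list, and the expected adverse events in section 15 include hypertension and atrial fibrillation under ivabradine. For the orthostatic test, section 14, item 4, says: "There may be an increased risk of hypotension or tachycardia upon changing positions from laying down to sitting to standing". Section 15 lists acute hypotension for the same test.

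**Measurements specified.** Section 9, Specific Protocols, gives two orthostatic readings, both of heart rate: "First, the patient's heart rate will be measured at rest after lying down for 3 minutes", and "Then, the patient will be asked to stand and the standing heart rate will be measured after 3 minutes". At Visit 4, "orthostatic heart rate monitoring, NE bloodwork, and QOL questionnaires will be completed". Visit 7 has the same content. Visits 3 and 6 have orthostatic heart rate and titration.

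**Analysis.** Section 9, Statistical Analysis, names mean heart rate, maximum heart rate and quality-of-life scores.

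**Safety section.** Under AE Management, item 3, the responsible clinician "will continuously monitor and oversee the procedure by checking vital signs" during orthostatic monitoring. Items 1 and 2 also mention vital signs, at blood draws and at the tilt test.

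**Eligibility.** Exclusion h in section 10 covers a resting heart rate below 60 beats/min and also "atrial fibrillation, advanced AV blocks, sinus disease, and acute decompensated heart failure". No visit description names an ECG or rhythm recording.

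**The concern.** The visit schedule and the safety section do not agree on what is measured. The first specifies heart rate, blood tests and SF-36. The second assumes that someone is watching vital signs. A site following section 9 to the letter would produce no blood-pressure data, and one following section 15 might look at blood pressure without keeping it.

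What is at stake is mainly the drug-placebo comparison of a named risk. A crossover gives each patient a placebo period to set against the ivabradine period, but only for values that are written down under the same conditions. Three features of this plan add to the cost of not recording them:

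- There is no DSMB. The investigator's aggregate adverse-event review can use only what was captured.
- Patients taking midodrine or Florinef are washed out for one week before baseline (section 9, Assessments). Section 7 says that both drugs can cause supine hypertension. Baseline blood pressure may therefore shift for reasons unrelated to ivabradine, which makes the comparison with placebo more useful than casual observation.
- The protocol's definition of POTS requires the absence of postural hypotension (sections 5 and 7). Heart rate alone cannot show this at follow-up.

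For rhythm, a symptom-free arrhythmia could go unnoticed. A heart rate taken during one would enter the primary endpoint like any other reading. The documents give no frequency for this, so its effect cannot be sized.

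**Working it through.** The plan gives no figure on this point, so the main check sets its sections side by side.

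**1. Each listed ivabradine reaction against what section 9 schedules**

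| Reaction | Scheduled measurement that would show it |
|---|---|
| Bradycardia | Lying and standing heart rate, Visits 1 to 7 |
| Visual distortions | Symptom, by patient report |
| Hypertension | None named |
| Atrial fibrillation | None named |

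Two of four have no named measurement.

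**2. What the vital-sign checks add.** Orthostatic monitoring is scheduled at all seven visits, so the check in AE Management item 3 reaches on-treatment Visits 3, 4, 6 and 7. Blood is drawn at Visits 1, 2, 4, 5 and 7. If vital signs include blood pressure (the ordinary reading, but an assumption here), a raised value could be seen at every visit. The adverse-event definition in section 15 covers signs as well as symptoms, so such a value could be reported. Four things are still missing: which signs are taken, in what position and when, whether they are entered on a form, and whether they are summarised by treatment. For rhythm, a pulse check might reveal irregularity by chance but would not identify atrial fibrillation.

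**3. What the existing procedure could supply**
- Per patient: 2 positions × 7 visits = 14 readings.
- On treatment: 2 positions × 4 visits (3, 4, 6, 7) = 8 readings, of which 4 are on ivabradine and 4 on placebo.
- For the planned 20 patients: 20 × 14 = 280 readings if all complete.

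**4. What event counts alone could show.** Section 10 expects 20 × (1 − 0.10) = 18 patients for final analysis. With every one measured on ivabradine and no events seen, the one-sided 95% upper limit on the event rate is

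1 − 0.05^(1/18) = 0.153, about 15%

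(with 20 patients, 1 − 0.05^(1/20) = 0.139). The documents give no event rate, so I assume a range. The chance of at least one event among 18 is 1 − (1 − p)^18:

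| Assumed rate p | Chance of at least one event |
|---|---|
| 1% | 0.165 |
| 5% | 0.603 |
| 10% | 0.850 |

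Counts of hypertension or atrial fibrillation would therefore be weak evidence even with full measurement. The useful information is blood pressure as a continuous variable, compared within patient, and that needs recorded values.

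**The case against.** The strongest reply is that the plan does look. Vital signs are checked under continuous monitoring at a procedure held at every visit, acute hypotension is an expected event of that procedure, and signs count as adverse events. This stands. A reader might infer that hypertension and atrial fibrillation could be found only through symptoms, but the safety section does not support that.

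Two other tempting readings also fail:

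- A reader might take the tilt test to be the only continuously monitored test, done only before the first dose. Orthostatic monitoring is described in the same terms. A tilt test is also attempted at drop-out, and Assessments speaks of tilt testing before and after treatment, although the visit list has it only at Visit 2.
- A reader might take the form contents in section 16 as proof that blood pressure is not recorded. That list is not exhaustive. It omits heart rate and SF-36 as well, which are plainly to be collected.

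Nor are the rhythm exclusions wholly unsupported. Section 15 requires a history and physical examination, medical records are screened for these conditions, and a monitored tilt test precedes randomisation.

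The reply does not supply a specified, recorded and analysed blood-pressure measurement. An unrecorded check can prompt care for one patient, but it cannot support a comparison of ivabradine with placebo.

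**Conclusion.** The point holds as a gap in specification. Two of the four listed ivabradine reactions have no named measurement in the visit schedule, the orthostatic procedure or the analysis. For blood pressure, the vital-sign checks allow chance detection but give no systematic data by treatment. For rhythm, no recording is named at any visit, so a symptom-free arrhythmia could be missed.

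This is a cheap improvement to safety data. It does not invalidate the primary comparison, and no section plans to report these risks as absent. The 15% limit also shows that fuller measurement would not let 18 patients rule out uncommon events.

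The verdict rests on the available text. Figure 1 and the uploaded ivabradine information document were not seen. If either lists blood pressure or an ECG by visit, the gap narrows to recording and analysis. That vital signs include blood pressure is assumed, since the protocol does not itemise them.

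**What to change.** Reconcile section 9 (Study Visits, Specific Protocols, Assessments) with AE Management in section 15:

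1. State which vital signs are taken. Record blood pressure with each existing lying and standing heart-rate reading at Visits 1 to 7.
2. Enter the values on the case report form.
3. Add blood pressure to the Statistical Analysis section: summaries by treatment, and the within-patient difference between ivabradine and placebo, lying and standing.
4. State whether and how rhythm is checked, both for the exclusions in section 10 and for atrial fibrillation as an adverse event. Whether to schedule ECGs, and when, is for the investigators.

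Cost: two cuff readings and a few form fields per visit, within a procedure already held, plus one more table in the analysis. No extra visit is needed, and no dose or stopping rule changes. If only one change is made, it should be the blood-pressure entry.

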### **Specific Aim 1: Evaluate the change in heart rate**

*Hypothesis: Ivabradine will reduce tachycardia and improve functional status in patients with POTS.*

We propose to test this hypothesis in a randomized double-blind placebo-controlled with a cross over clinical trial in which otherwise healthy patients diagnosed with POTS will be randomized into Ivabradine or placebo group treatment for one month then crossed over to the other group for another month (one week wash-out period before cross over). Patients will undergo a baseline tilt table test, norepinephrine bloodwork, and quality of life (QOL) questionnaires.

- Primary endpoint:
  - Change in heart rate after one month of Ivabradine intervention compared to baseline.
- Secondary endpoint:
  - Quality of life measured with questionnaires after one month of Ivabradine intervention compared to baseline.

We will assess:

- *Effects on tachycardia (table tilt test)*
- *Orthostatic heart rate monitoring*
- *Symptomatic changes (QOL questionnaire)*

*Results will provide significant understanding of mechanisms that underlie sympathetic hyperactivation and provide a potential avenue for an effective and safe treatment with Ivabradine with the ultimate goal of increasing patient adherence and reducing debilitating patient symptoms.*

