who are infertile will not be asked to take pregnancy test per PI discretion. The patient will be instructed to begin the secondary treatment (placebo or Ivabradine) for one month.

-At Visit 6, two-weeks into this treatment, the patient will return to ACTRI for drug titration. Orthostatic heart rate will be monitored. If the patient fulfills criteria (see **Ivabradine Dosing** below), they will either increase, decrease, stop, or not change their Ivabradine dose.

-At Visit 7, one month after starting the secondary treatment, the patient will return for orthostatic heart rate monitoring, NE bloodwork, and QOL questionnaires.

Blood samples will be saved and securely stored with the PI for future research analysis and purposes.

**Randomization.** Randomization refers to the order in which patients receive placebo or Ivabradine. If a patient receives Ivabradine first for one month, then he/she will be switched over to placebo for one month. If a patient receives placebo first for one month, then he/she will be switched over to Ivabradine for one month. There will be a one-week washout period prior to the cross-over. There will be 10 patients in each group.

**Ivabradine Dosing.** Ivabradine dose will initiate at 5mg twice daily (bid) and be increased to 7.5mg twice daily (bid) after 2 weeks if the heart rate is greater than 70 beats/min. If the heart rate is less than 70 beats/min there will no increase in dose. If the heart rate is less than 50 beats/min, or if the patient has symptoms of dizziness or lightheadedness, then Ivabradine will be stopped.

If patients have side effects and feel that cannot continue with Ivabradine we will decrease the dose from 7.5mg bid to 5mg bid (or if they are on 5mg bid to 2.5mg bid). After this dose reduction if the patient is still unable to tolerate Ivabradine, we will stop Ivabradine and withdraw patient from the study. If a patient is unable to tolerate Ivabradine (particularly prior to crossover period), he/she will be withdrawn. The starting dose and titration model is the same for the crossover treatment period as the initial month.

In our clinical experience using Ivabradine in patients with inappropriate sinus tachycardia (which are very similar to POTS patients in age and co-morbidities) we have not seen significant side effects that have caused patients to stop the drug. Refer to the uploaded Ivabradine Drug Information document for more details.

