**Statistical Analysis.** Continuous variables including mean heart rate, maximum heart rate, and quality of life scores will be summarized using descriptive statistics, including the number of observation (n) mean, standard deviation (SD), standard error (SE), median, the 1st (Q1) and 3rd (Q3) quartiles, minimum, and maximum values. The change in heart rate at one month from baseline will be compared by T-tests based on treatment status with placebo versus Ivabradine. Categorical variables will be compared by McNemar's test based on treatment status with placebo versus Ivabradine.

The study design will be adaptive and data analysis will be done in batches. The PI and others involved in data analysis will be blinded to who is the Ivabradine group and who is in the placebo group.

**Power Analysis.** Assuming a decrease in average heart rate of 10 beats/min is clinically significant (e.g. Decrease from 100 to 90; magnitude of effect 10%) with power 0.8 and standard deviation in heart rate is 7.5 beats/min, the estimated sample size is 18 patients. We will enroll 10 patients in each group to account for the 10% drop-out rate and to ensure the study is adequately powered. For sample size calculation, two-sided alpha level = 0.05 and two sample t-test are used.

**Drop-outs.** If any patient decides to withdraw from the study due to the intolerance of side-effects, we will try to obtain a tilt table test, orthostatic heart rate, QOL questionnaire, and blood tests at the time of drop-out.

**Documentation.** All patient related documentation will be stored at UCSD for future analysis as funding becomes available. To minimize the potential loss of confidentiality, patients will be assigned a unique number as their subject identifier code. The unique subject code will be used to label all study documents. The key that relates the code numbers to the individuals will be kept in a locked cabinet in the PI's office at the ACTRI.

All procedures mentioned above are research procedures and are not part of standard care.

Results may be used for diagnosis, treatment, and prevention of disease in patients.

**Incidental findings that result from the conduct of this study that require medical intervention for the subject will be noted by the PI or her project's medical research staff. They will refer the subject to his primary care physician. If the subject does not have a primary care physician one will be appointed for him or her.**

---

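### The crossover is sized as two parallel groups, and the primary t-test leaves pairing, period adjustment and the second-period baseline open

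*Combined protocol and SAP*

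**What the plan says.** The design is a two-sequence, two-period crossover with a one-week washout. Under Randomization in section 9: "Randomization refers to the order in which patients receive placebo or Ivabradine". Ten patients are planned per sequence.

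The Power Analysis paragraph takes a difference of 10 beats/min and continues "with power 0.8 and standard deviation in heart rate is 7.5 beats/min, the estimated sample size is 18 patients". It names the test: "For sample size calculation, two-sided alpha level = 0.05 and two sample t-test are used". Twenty are enrolled to allow for 10% drop-out. Sections 10 and 11 describe the remaining 18 as giving adequate power.

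The primary endpoint in Specific Aim 1 is "Change in heart rate after one month of Ivabradine intervention compared to baseline". Its analysis, under Statistical Analysis in section 9, is "The change in heart rate at one month from baseline will be compared by T-tests based on treatment status with placebo versus Ivabradine". The next sentence covers other data: "Categorical variables will be compared by McNemar's test based on treatment status with placebo versus Ivabradine".

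On baseline, the Visit 2 description says "A tilt table test will be performed to determine baseline heart rate". Orthostatic heart rate is also taken at Visit 2. After washout, "At Visit 5, the patient will return for orthostatic heart rate monitoring", just before the second treatment starts. Visit 5 is not called a baseline.

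**The concern.** In a crossover each patient is his or her own control, so the SD that governs precision is that of the within-patient difference between treatments. The plan gives no such SD and no correlation from which to derive it. It uses an SD of heart rate in a calculation for separate groups, so the stated power of 0.8 does not describe the trial's natural analysis.

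The analysis sentence is open on three points:

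- **Pairing.** McNemar's test is a paired method and hints at pairing, but it covers categorical variables only. The one type of t-test the plan names, for sizing, is two-sample.
- **Period.** No period term is mentioned.
- **Second-period baseline.** Visit 2 and Visit 5 are both available, and the choice changes the precision of the primary result.

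Section 9 also says the data will be analysed in batches. Results could therefore be visible while these choices remain open.

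**Working it through.** **Inputs.** From section 9, Power Analysis: difference 10 beats/min, SD 7.5 beats/min, two-sided alpha 0.05, power 0.8, 18 evaluable and 20 enrolled. The correlation ρ between two heart rates in one patient is not in the documents. It is assumed equal between all visits and varied from 0 to 0.7.

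**1. The plan's figure.** For two independent groups, by normal approximation:

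n per group = 2(1.960 + 0.842)²(7.5/10)² = 8.83, so 9 per group and 18 in total; 18/0.9 = 20.

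The figure reproduces. Normal-approximation power at 9 v 9 is 0.807. For the t-test itself the standard error is 7.5√(2/9) = 3.54 and the noncentrality 10/3.54 = 2.83 on 16 df, giving power 0.757. At 10 v 10 (all 20 evaluable) it is 0.805.

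**2. Which SD is 7.5?** The endpoint is a change. If 7.5 is the SD of one measurement, the SD of a change is 7.5√(2(1−ρ)), which equals 7.5 only at ρ = 0.5. Applied to changes, the 9 v 9 calculation has power 0.61, 0.76 and 0.93 at ρ = 0.3, 0.5 and 0.7.

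**3. Within-patient analysis.** Take 18 completers, 9 per sequence, and a period-adjusted test with 16 df and standard error SD_d/√18. The half-width is 2.120 × SD_d/√18.

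- Common Visit 2 baseline: the baseline cancels, so SD_d = 7.5√(2(1−ρ)).
- Period-specific baselines (Visits 2 and 5): SD_d = 7.5√(4(1−ρ)), which is twice the variance.

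**4. Unpaired analysis of common-baseline changes.** Here 18 v 18 values are treated as independent; half-width = 2.032 × 7.5√(2(1−ρ)) × √(2/18).

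| ρ | Common: SD_d | Power for 10 | Half-width | Period-specific: SD_d | Power for 10 | Half-width | Unpaired, common: half-width |
|---|---|---|---|---|---|---|---|
| 0 | 10.61 | 0.963 | 5.30 | 15.00 | 0.757 | 7.49 | 7.19 |
| 0.3 | 8.87 | 0.994 | 4.43 | 12.55 | 0.887 | 6.27 | 6.01 |
| 0.5 | 7.50 | 0.9996 | 3.75 | 10.61 | 0.963 | 5.30 | 5.08 |
| 0.7 | 5.81 | >0.999 | 2.90 | 8.22 | 0.998 | 4.11 | 3.94 |

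At ρ = 0.5 the difference detectable with 80% power is 5.28 beats/min (common) against 7.46 (period-specific).

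The unpaired interval is wider than the within-patient one by 2.032√(2/18) ÷ (2.120/√18) = 1.36 at any ρ. In simulation with no treatment effect (60,000 data sets per setting), the unpaired test rejected about 0.8% of the time with a common baseline and 5.0% with period-specific baselines. In the latter case equal correlations make the two changes uncorrelated, so pairing gains nothing. The period-adjusted test rejected about 5% in both.

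**5. Leaving out the period term.** Assume a period effect of 5 beats/min and SD_d = 7.5. A paired test without adjustment then has a false-positive rate of about 2.0%. Its power for a true difference of 5 beats/min is about 61%, against 75.7% with adjustment. With 10 v 8 completers its estimate is biased by 5 × 2/18 = 0.56 beats/min.

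**6. Power by SD of the within-patient difference** (18 completers, 10 beats/min): 0.9996 at 7.5, 0.978 at 10, 0.890 at 12.5 and 0.757 at 15. It stays at or above 0.80 up to 14.2.

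**The case against.** The sizing error is conservative. From a common baseline, within-patient power for 10 beats/min is at least 0.963, and even the unpaired reading has simulated power of about 0.86, 0.96 and 0.995 at ρ = 0, 0.3 and 0.5. The period-adjusted crossover test can itself be written as a two-sample t-test of period differences between the two sequences. On that view the plan's calculation equals it at SD_d = 15, since 15/√18 = 7.5√(2/9), and so acts as a bound. The gap between 0.757 and 0.80 is the normal approximation. None of the readings checked inflates the false-positive rate. Analysts are to be blinded, the word baseline is attached only to pre-randomisation tests, and McNemar's test points to pairing. The doubling of variance also depends on equal correlations: the ratio is 4(1−ρ_within)/[2(1−ρ_between)], which is 1.2 at 0.7 within a period and 0.5 between periods, and 1.0 at 0.75 and 0.5.

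Most of this stands as a limit on the harm. The trial should not be called underpowered, and the cost of period-specific baselines could be smaller than shown. It does not supply the missing specification. The plan never says that 7.5 stands in for an SD_d of 15. Blinding limits steering towards ivabradine, but results under coded labels can still be seen before a method is chosen.

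**Conclusion.** The concern holds and should be fixed. The 18 is a parallel-group figure for a crossover trial. The stated 0.8 matches neither the exact power of the named test at 18 evaluable patients (0.757) nor a within-patient analysis from a common baseline (0.963 or higher). Pairing, period adjustment and the second-period baseline for heart rate are not settled anywhere in the document.

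The consequence is uncertain precision and an open choice, not a shortage of patients. At ρ = 0.5, half-widths run from 3.75 to 5.30 beats/min across readings of one sentence. The lowest power found for a within-patient test, 0.757, needs period-specific baselines and zero correlation.

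The effect and the SD are the plan's. The correlations, their equality between visits, the reading of 7.5 as a per-measurement SD and the period effect are assumptions. It cannot be said that the analysis will be unpaired, only that the plan does not exclude it.

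**What to change.** Replace the t-test sentence in section 9 with wording such as:

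> *Heart-rate change from the pre-randomisation Visit 2 value to the end of each treatment month (Visits 4 and 7) will be compared between ivabradine and placebo within patient, by a paired t-test adjusted for period, two-sided 0.05. The same heart-rate measure will be used at Visits 2, 4 and 7.*

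A mixed model with treatment, period and sequence and a random patient effect is an acceptable alternative. Choose one as primary before any data are analysed, because the two can use different patients when someone completes only one period.

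The plan should name the heart-rate measure. Orthostatic heart rate is scheduled at all three visits; the tilt test is scheduled only at Visit 2. The Visit 2 value cancels from the within-patient contrast, so the endpoint can still be reported as a change from baseline.

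Restate the power paragraph for this analysis, for example:

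> *With 18 patients completing both periods, power for 10 beats/min is 0.98, 0.89 or 0.76 if the SD of the within-patient difference is 10, 12.5 or 15 beats/min.*

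If the two-sample calculation is kept, give its power as 0.76 at 18 evaluable patients.

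The cost is the wording of two paragraphs, with no added patients, visits or measurements.
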